9.2.5 Validation of Self-Reported Events

A self-administered questionnaire used by study participants at short intervals is a sensitive tool which captures almost all serious clinical outcomes [1]. From a methodological point of view, it captures a much higher proportion of these outcomes than methods relying only on the prescribing health care professional who often is not involved in the diagnosis and treatment of these outcomes. However, it must be considered that there is a significant difference between the rates of reported and validated events, because laypersons often misclassify adverse events. Therefore, validation of the self-reported events is of utmost importance.

Validation of self-reported events will start at the level of the local field organizations with a review of all subject-reported "events." This will be followed by a further review at the international coordinating center (ZEG).

If an adverse event is reported by a study participant, the subjectively perceived symptoms, the signs of disease and if possible the diagnosis as understood by the study participant are

¹⁸ Or at the end of the study if the study ends prior to the 24 month follow-up of an individual patient.

¹⁹ Serious adverse event means any AE that results in death, a life-threatening experience, inpatient hospitalization, persistent or significant disability/incapacity, or requires medical/ surgical intervention to prevent one of said outcomes.

to be recorded on the follow-up questionnaire. The name and address of the relevant physician (attending physician, physician responsible for the follow-up treatment after discharge from hospital, or primary care physician) are also documented.

Follow-up questionnaires containing information on such an event are to be immediately passed on to the medical reviewer group at ZEG. If information is unclear or missing the woman will be contacted by phone, e-mail or other means. For many serious events it will be necessary to contact the diagnosing and/or treating physician for clarification and validation of the information received from the patient.

Under routine medical conditions, diagnosis of an SAE term is not always confirmed by a diagnostic method with high specificity. Therefore, SAEs are classified by the investigators as “confirmed” or “not confirmed” according to a predefined algorithm (cf. Section 9.10.1).

In order to minimize classification bias - particularly if selectively affecting an individual exposure cohort - classification of self-reported serious cardiovascular outcomes, into confirmed and not confirmed cases will be adjudicated by three independent medical experts specializing e.g. in radiology/nuclear medicine, cardiology, and internal medicine/phlebology. They will review all available information on the reported outcomes. For this process, the adjudicators will be blinded to the brand names and composition of the treatments used by the reporting woman. The adjudicators will perform the reviews independently of each other and without knowing the judgement of the other adjudicators or the investigators. Details of the procedure are given in Section 9.10.2.

In addition, the ZEG physician who is responsible for the assessment of individual case reports prior to interim analyses will be blinded to the study drug (i.e. he/she will do his/her assessment based on redacted copies of the available documents). Also individual case reports that are presented to the Safety Monitoring and Advisory Council will be blinded to the study drug.

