Combined oral contraceptives (COCs) became available in the early 1960s and are - with currently about 100,000,000 users worldwide – the most popular form of effective, reversible contraception available. However, alternative methods for hormone administration have been investigated and are widely used, including injections, implants and intrauterine devices. To broaden the choice of female contraceptive methods, the transdermal route through the use of a patch has been developed because of its potential benefits. With respect to compliance, a patch only has to be applied once per week (three weeks active patch plus one week break, i.e. 21/7 day cycle). This is likely to facilitate its compliant use, especially in women who find it difficult to adhere to a daily intake regimen [1].

From a pharmacological point of view, the development of a patch for hormonal contraception is based on the rationale that active substances given via a transdermal route are not subject to first pass metabolism in the liver; thus, effective serum levels can be achieved with lower total drug exposure, especially with substances of reduced oral bioavailability like ethinyl estradiol (EE). Transdermal formulations provide more stable levels of the active substances in the body, in contrast to oral preparations, which give rise to fluctuations and high peak concentrations. Furthermore, the drug delivery via the transdermal route is unaffected by gastrointestinal complaints such as vomiting and diarrhea. To date, the only contraceptive control patch available on the market is the EE and norelgestromin (NGMN) patch, approved in the US (Ortho Evra) and in Europe (Evra).

The newly developed FC Patch Low consists of a fixed combination of ethinyl estradiol (EE) and gestodene (GSD). The estrogen component, EE, is the standard estrogen used in nearly all combined OCs. It provides acceptable skin permeability and offers efficacious cycle control. The progestin component, GSD, has been extensively used in a wide variety of OCs and products for hormone therapy for over 25 years and has a well-known efficacy and safety profile. GSD was selected based on its high progestogenic potency per weight of the progestin [2] and its good skin permeability, which is unique in comparison to other progestins and renders it specifically suitable to be chosen in a patch application. In comparison to other progestins, GSD also offers particularly good cycle control.

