9.2.1 Treatments

- Cohort 1:** FC Patch low, a transdermal patch containing 2.1mg of gestodene and 0.55mg of ethinyl estradiol
- Cohort 2:** Levonorgestrel-containing COCs: 1) monophasic preparations containing 20 – 30mcg of ethinylestradiol; 2) multiphasic preparations containing up to 40mcg of ethinylestradiol

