This study combines several methodological strengths that are substantial for the validity of the results: i) prospective, comparative cohort design; ii) availability of important confounder information (e.g., BMI and family history of VTE); iii) validation of outcomes of interest and the exposure of the relevant cases; iv) comprehensive follow-up procedure and very low loss to follow-up to minimize underreporting; v) independent, blinded adjudication of VTE cases; vi) relevant statistical analyses (e.g., stratified analyses by user status and exposure period; comparison of isochronous, new user cohorts; sensitivity analyses on the impact of the adjudication process, outcome definition, and prognostic factor/covariate selection); vii) study population representative for oral contraceptive users under routine clinical conditions; viii) generalizability of results as hormonal contraceptive use in this study reflects routine clinical use and study participation is not limited by medical inclusion and exclusion criteria; ix) supervision by an independent Safety Monitoring and Advisory Council, and scientific independence from the study funder.

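### The adjudicators' blind covers brand and composition but not route or dosage form, so in a patch-versus-pill study the text does not secure concealment of the cohort

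*Protocol*

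**What the plan says.** Protocol section 9.2.5 gives the purpose of adjudication: "In order to minimize classification bias - particularly if selectively affecting an individual exposure cohort". Three independent experts classify self-reported serious cardiovascular outcomes. On their material it says "They will review all available information on the reported outcomes", and on masking it says "the adjudicators will be blinded to the brand names and composition of the treatments used by the reporting woman". It refers to section 9.10.2 for details, but that section sets out only the voting steps and six ways of combining the votes. It adds nothing on masking.

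The next paragraph of 9.2.5 uses a different standard for the ZEG physician who assesses cases before interim analyses. That person is blinded to the study drug, and "he/she will do his/her assessment based on redacted copies of the available documents". Case reports for the Safety Monitoring and Advisory Council (SMAC) are also blinded to the study drug. No redacted copies are mentioned for the adjudicators.

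Section 9.2.1 defines the cohorts: "FC Patch low, a transdermal patch containing 2.1mg of gestodene and 0.55mg of ethinyl estradiol" against "Levonorgestrel-containing COCs". Section 9.9 lists "independent, blinded adjudication of VTE cases" among the study's strengths.

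**The concern.** Masking brand and composition is a reasonable rule when one pill is compared with another. Here the two cohorts differ by route. A record redacted exactly as the rule says can still mention a patch, a pill, weekly application or a skin reaction, and each of these points to one cohort.

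Adjudication decides which events count in the primary hazard ratio. If an adjudicator can tell the cohort, a prior belief about the new patch can move the confirmation threshold in one cohort only. That is the cohort-selective classification bias that section 9.2.5 says adjudication is there to prevent. Section 9.9 already accepts that heightened awareness may lead to more VTE being detected with a new product. A blind that leaves the route visible lets the same awareness act a second time, at the adjudication stage.

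**Working it through.** **1. Does the stated rule conceal the cohort?**

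- Masked for adjudicators (9.2.5): brand names and composition.
- Not mentioned for adjudicators in 9.2.5 or 9.10.2: route, dosage form, application regimen, redacted copies.
- Material: all available information. Section 9.2.4 says follow-up of reported events includes hospital records, discharge summaries and concomitant medication.
- Products: section 7 says "the only contraceptive control patch available on the market is the EE and norelgestromin (NGMN) patch". A visible reference to a patch therefore leaves FC Patch Low or, after a switch, one other product. A visible reference to a pill rules FC Patch Low out.

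The rule as written leaves words in place that largely reveal the cohort.

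**2. Reproducing the plan's event number**

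Inputs from section 9.5: margin 1.5, one-sided alpha 0.05, power 0.80, true hazard ratio 1. Recruitment is 1:1 (section 9.2.2). By the Schoenfeld formula:

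D = 4 × (1.6449 + 0.8416)² / (ln 1.5)² = 4 × 6.183 / 0.1644 = 150.4

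The protocol's 150 is reproduced, and power at 150 events is 79.9%. The sample size is not in question. With an even split, SE(log HR) = √(4/150) = 0.163, and non-inferiority needs an observed hazard ratio of at most exp(0.4055 − 1.645 × 0.163) ≈ 1.147.

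**3. What a differential confirmation rate would do**

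Let r be the ratio of confirmation probabilities, patch to pill. The protocol gives no value, so every r other than 1 is an assumption. Hold confirmed events at 150, and set h = true HR × r, p = h/(1 + h) and SE = √(1/(150·p·(1 − p))). The probability of concluding non-inferiority is Φ[(ln 1.5 − ln h)/SE − 1.645].

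| True HR | r | HR seen on average | Probability of concluding non-inferiority |
|---|---|---|---|
| 1.0 | 1.00 | 1.00 | 79.9% |
| 1.0 | 1.05 | 1.05 | 70.5% |
| 1.0 | 1.10 | 1.10 | 60.0% |
| 1.5 | 1.00 | 1.50 | 5.0% |
| 1.5 | 0.95 | 1.425 | 9.1% |
| 1.5 | 0.90 | 1.35 | 15.7% |

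For r = 1.10 at true HR 1.0: SE = 0.1635, and (0.4055 − 0.0953)/0.1635 − 1.645 = 0.25, which gives 60%. At true HR 1.0, half of 150 events is 75 patch cases, so a 5% or 10% shift is about 4 or 8 cases (75 × 0.05 = 3.75; 75 × 0.10 = 7.5).

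**4. Which direction is more plausible?**

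The final analysis uses strategy V of section 9.10.2: one vote of three, cast before discussion, confirms a case. If each adjudicator confirms with probability q and votes are independent (a simplification), the case is confirmed with probability 1 − (1 − q)³.

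- Case that is not a true event: q rising from 0.05 to 0.10 takes case-level confirmation from 14.3% to 27.1%.
- True event: q = 0.80 gives 99.2%. A 10% relative fall, to 89.3%, needs (1 − q)³ = 0.107, so q ≈ 0.52. Correlated votes would need a smaller drop.

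Strategy V is therefore much more open to over-confirmation than to under-confirmation.

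**The case against.** A reader might infer that the blind cannot hold, or that adjudicators will know every woman's cohort. The protocol does not support that. It is silent on route and does not say that route will be disclosed. Section 9.8 mentions standardized working procedures for the Blinded Adjudication Board. Those procedures are not shown and may remove route. Women may also switch to another hormonal contraceptive (section 9.2.2), and the primary analysis assigns events to the treatment in use at the time. A pill is therefore not necessarily a levonorgestrel pill, and a patch could be the other marketed product. All this limits the claim. It does not repair a protocol rule that states its own, narrower scope.

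A reader might also take the 16% false non-inferiority figure as the headline. Strategy V argues against that, because under-confirmation requires all three independent adjudicators to reject.

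The algorithm in section 9.10.1 leaves limited discretion. Definite VTE rests on imaging, and an attending physician's confirmation is enough for a probable case; neither criterion depends on the contraceptive. This stands for imaging-confirmed cases. The probable category, which counts as confirmed, can also rest on a clinical diagnosis or a non-imaging test, and there judgment remains.

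Finally, the ZEG physician's separately blinded assessment and the sensitivity analyses on adjudication listed in section 9.9 offer a comparison. They would help to show a problem, but would not remove a bias shared by all three adjudicators.

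**Conclusion.** The point holds as a gap in a stated rule. For a comparison of a patch with a pill, masking only brand and composition falls short of the purpose that section 9.2.5 gives for adjudication, and the strength claimed in section 9.9 is not secured by the text. Identification through route is likely but not certain.

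The direction and size of any bias are unknown. The more likely distortion is over-confirmation of patch cases in the probable category. That pushes the hazard ratio up and costs power (about 80% down to 70% or 60% in the table) rather than producing a false claim of safety. The opposite direction is possible but harder to reach. These figures rest on assumed shifts of 5% and 10%, 150 confirmed events and a Wald test on the log hazard ratio. They show sensitivity and are not a forecast.

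It should not be inferred that the ZEG physician and the SMAC case reports share the narrow wording. Both are already blinded to the study drug; it is only unstated whether this covers route and form.

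**What to change.** - **Section 9.2.5, adjudicators:** extend the blind to all information that identifies the contraceptive, its route, its dosage form or its regimen, replaced by a neutral term such as combined hormonal contraceptive. State that adjudicators work from redacted copies, as the ZEG physician already does.
- **Section 9.10.2:** add a cross-reference to this rule. The section has no masking wording of its own to replace.
- **Section 9.2.5, ZEG physician and SMAC:** clarify that blinding to the study drug covers route and form, both for case confirmation and for the case reports. Keep the causality assessment (section 9.10.3) separate, because it needs the drug's identity.
- **Optional:** have each adjudicator record whether the route could be inferred, so that the blind can be checked.

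The cost is a wording change, a longer list of terms to redact and a modest amount of extra redaction work. Redaction is already planned for the ZEG physician's copies. The rule is best settled before data collection starts, because case assessments for interim analyses come before the final adjudication.

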9.2.6 Loss to follow-up

A low “loss to follow-up rate” will be essential for the validity of the study. In order to minimize loss to follow-up a multi-faceted, four-level follow-up process will be established. Level 1 activities include mailing of the follow-up questionnaire and – in case of no response – up to two reminder letters. If level 1 activities do not lead to a response, multiple attempts are to be made to contact the woman, friends, relatives and the gynecologist/primary care physician per phone. In parallel to these level 2 activities searches in national and international telephone and address directories as well as electronic social networks are started (level 3 activities). If this is not successful, an official address search via the respective governmental administration and commercial databases will be conducted. This level 4 activity can provide information on new addresses (or emigration or death). The aim is to keep the total loss to follow-up at the end of the study at less than 5% of the study

population. The EURAS study [3] has demonstrated that the chosen study design is suitable to reach this goal.

9.3 Variables

9.3.1 Primary Endpoint

Venous Thromboembolism (VTE)

Deep venous thrombosis (DVT) and pulmonary embolism (PE) are the most relevant adverse drug reactions associated with combined hormonal contraceptive use. Based on a request of the European regulatory authorities specific VTEs - DVT of the lower extremities and pulmonary embolism - was chosen as the primary outcome of interest (cf. Section 8). Inferential statistics will be based on the VTE hazard ratio for FC Patch Low vs. COC_{LNG} (cf. Section 9.2.1).

Information about the use of the new FC Patch Low is only available from clinical trials including a limited number of study participants. It consists of a fixed combination of ethinyl estradiol (EE) and gestodene (GSD). The estrogen component, EE, is the standard estrogen used in nearly all combined OCs, and the progestin component, GSD, has been extensively used in a wide variety of OCs and products for hormone therapy for over 25 years with a well-known efficacy and safety profile. The combination of EE and GSD is used for many OCs marketed in the European Union (EU) and considerable experience has already been documented for this combination and oral route of administration.

VTE and ATE are well-known side effects of hormonal contraceptives. No real-life data are available for the effect of the FC Patch Low on VTE and ATE. During the approval process, the MAH received the condition to prove that the FC Patch Low is not expected to have a negative impact on the risk of VTE and ATE compared to combined oral contraceptives (COC) containing LNG. Therefore, a prospective, controlled, non-interventional, long-term cohort study to assess the impact of short- and long-term risk was deemed appropriate. The study proposed in this protocol should provide data that are sufficiently robust to eliminate a 1.5-fold risk in VTE for FC Patch Low compared to COC_{LNG}. The comparator was specifically requested during the DCP of FC Patch Low.

During this study, information on known risk factors for VTE will be collected. This includes age, BMI, family history of VTE and current duration of use. Information on the smoking status (current, ever, never, number of cigarettes and period of smoking) and socio-economic status (highest level of education) will be collected as well although they are believed to have a minor influence. All potential confounding factors will be included in a multivariable model to test whether they change the strength of the association between exposure and outcome.

The main clinical outcomes of interest for the short (FU 1 after 6 months) and long-term follow-up (FU 2 after 12 months and FU 3 after 24 months) are venous thromboembolism (VTE), specifically:

- Deep Venous Thrombosis (DVT) of the lower extremities (ICD-10 codes: I80.1, I80.2); excluding I80.3
- Pulmonary Embolism (PE); this includes the ICD-10 codes I26.0 and I26.9

Furthermore, sensitivity analyses are planned in order to

- 1) evaluate the impact of including I80.3 (phlebitis and thrombophlebitis of lower extremities, unspecified), which means that DVT of the lower extremities plus I80.3 plus pulmonary embolisms are analyzed
- 2) all DVTs and pulmonary embolisms.

9.3.2 Secondary Endpoints

For several other clinical outcomes an association to hormonal contraceptive use has been discussed. For some outcomes a causal relationship has to be assumed (e.g., hormonal contraceptive use and myocardial infarction in women with a combination of risk factors - in particular smoking, advanced age and high blood pressure) for other outcomes the existing evidence is weak (e.g. prolonged time to conception after stop of hormonal contraceptive use). The selection of following secondary endpoints will be investigated in this study (cf. Section 8):

- All VTE
- Arterial Thromboembolism (ATE)
- 'Idiopathic' VTE (VTE cases with acute risk factors – such as pregnancy, delivery, trauma, immobilization, long-haul travel, surgery, chemotherapy – excluded)
- Cancer entities
- Application site reactions
- Pregnancy related outcomes
- Serious adverse events

Most of these secondary endpoints were successfully investigated in the EURAS study [1;4;5] and/or similar studies.

9.4 Data sources

This is a field study. Exposure to hormonal contraceptives, concomitant medication, primary and secondary outcomes, potential confounding factors and potential effect modifiers will be documented by the study participants, the recruiting and attending physicians in the

questionnaires and additional documentation sheets, if needed. Baseline data (cf. Section 9.2.3) will be recorded on a self-administered questionnaire containing questions relating to participants' state of health and potential risk factors. Participants will provide their medical history, including medication history and history of OC use. The information given by the study participants will be checked by their physicians.

In addition to the baseline variables described in Section 9.2.3 study participants will provide their addresses and phone numbers, as well as those of relatives or friends – who could serve as reserve contacts – and their primary care physician/gynecologist.

In line with data privacy regulations, these data will be documented on a separate sheet. During study conduct and study evaluation these sheets and the electronic representations of their content will be stored separately from the baseline questionnaires and their respective electronic representation. This also applies to the archiving of documents and databases at the end of the study.

Follow-up assessments for each woman in this study are scheduled 6, 12 and 24 months after study entry. Questionnaires will be mailed to the participating women, who often know more about their own personal health-related events than the physician who prescribes their OC. This is especially true for information on SAEs that were treated by other physicians. In some cases, events will be reported by the participant or by relatives, friends or attending physicians between the regular follow-ups. All reports – independent of the source of information – will be validated according to the process given below (cf. Section 9.10.1)

The follow-up questionnaires address the occurrence of adverse events – in particular serious adverse events. Reasons for contraceptive discontinuation or for a switch to another hormonal contraceptive (HC) will be requested if applicable as well as pregnancy related data to gather effectiveness information [4;5]. The variables that are recorded at each follow-up are described in Section 9.2.4.

The questionnaires will be collected in the participating countries by the local collaborators of ZEG, and will be reviewed for completeness and plausibility/consistency of the responses. Missing and inconsistent information will be clarified directly with the women via telephone. The completed questionnaires will be forwarded to ZEG. At ZEG all incoming data will be subjected to comprehensive quality control including electronic and manual plausibility checks. Unclear or inconsistent information will be described in detailed queries which will be forwarded to the local collaborators for clarification with the women. ZEG will monitor and endorse the timely processing of the queries.

The overall results and particularly the results on outcomes of interest will be reviewed by the Safety Monitoring and Advisory Board (cf. Section 10.3). The results of the validation process of reported outcomes of interest will be quality controlled by blinded adjudication (cf. Section 9.10.2).

